7.2 Reload Information

Product name 1	echelon 60 ENDOPATH STAPLER Endoscopic Linear Cutter Reloads
Specification/model 1	ECR60W
Registration No. 1	GXZJ 20153080094
Structural composition 1	The linear cutter stapler reload is composed of cartridge, anastomotic nail and reload-protecting board, in which the material of anastomotic nail is Ti3Al2.5V. The reload is sterilized by radiation and provided for single use.
Product name 2	ECHELON 45 ENDOPATH Stapler Endoscopic Linear Cutter and Reloads
Specification/model 2	ECR45M, EC45, SC45, ECLG45, ECR45W, ECR45B, ECR45D, ECR4 5G
Registration No. 2	GXZJ 20163654883
Structural	The product is composed of anvil, trigger, firing trigger, handle and cartridge
composition 2	component. The reload is sterilized by radiation and provided for single use.
Product name 3	ECHELON FLEX Articulating Linear Cutters and Reloads Articulating Endoscopic Linear Cutter Reloads
Specification/model 3	EC45A, SC45A, EC45AL, EC60A, SC60A, LONG60A, ECR60W, ECR 60B, ECR60D, ECR60G, ECR60T, ECR60M
Registration No. 3	GXZJ 20173656323

	This product is composed of stapler and cartridge. Its components include cartridge,
Structural	closing rod, firing rod, rotary knob, articulating piece, manual knife-reversing switch,
	trip count indicator, knife direction indicator, anvil release button, closing rod, and
composition 3	anvil. The stapler is made of stainless steel, and the anastomotic needle is made of
	titanium alloy (Tianium3A12.5V). The product is sterilized by radiation.
	It is used for transection, resection and/or anastomosis. It can be used in a variety of
	open or minimally invasive general, gynecologic, urologic, thoracic, and pediatric
Applicable scope	surgical procedures. It can be used with staple line or tissue buttressing materials.
	These devices can also be used for transection and resection of liver parenchyma
	tissues (hepatic vasculature and biliary structures), pancreas, kidney and spleen.
Manufacturer	Ethicon Endo-Surgery, LLC
Agent	Johnson & Johnson Medical (Shanghai) Ltd.

8. Overall Design

8.1 Test Design

8.1.1 Primary objective

To evaluate whether the primary effectiveness evaluation indicator "anastomosis success rate" of the Disposable Powered Articulating Endoscopic Linear Cutter Stapler manufactured by Fengh Company is non-inferior to the similar product manufactured by Johnson & Johnson Company in gastrointestinal tissue cutting and anastomosis.

8.1.2 Secondary objectives

To evaluate whether there are differences in the secondary evaluation indicators when the Disposable Powered Articulating Endoscopic Linear Cutter Stapler manufactured by Fengh Company is used in gastrointestinal tissue cutting and anastomosis compared with the similar product manufactured by Johnson & Johnson Company.

To evaluate whether there are differences in the safety evaluation indicators (e.g., incidence of AEs, incidence of SAEs, incidence of device defects) between the Disposable Powered Articulating Endoscopic Linear Cutter Stapler manufactured by Fengh Company and the similar product manufactured by Johnson & Johnson Company in gastrointestinal tissue cutting and anastomosis.

8.1.3 Selection of test method and reasons

This clinical trial is a "prospective, multi-center, stratified-block randomization, incomplete blinding, parallel

positive control, non-inferiority test".

- (1) Prospective: A research method that tracks from the present to the future. Prospective studies can clarify the causal relationship; uniform diagnostic, detection, and evaluation criteria can be available for the obtained data, the data processing therefore is controllable.
- (2) Multi-center: 5 clinical trial institutions were selected to conduct this clinical trial. The application of multi-center trial can allow to obtain more cases than those of single-center trial in the same time, the clinical trial time therefore can be shortened; since the multi-center trial is completed by different regions, different trial centers and many clinical researchers, the conclusion therefore is often widely representative.
- (3) Stratified block randomization: This trial adopts the stratified block randomization method (with the study site as the stratification factor) and the randomization envelope to randomize the subjects who are screened successfully. The randomized-grouping time is when the subjects sign the ICF, which also meets the inclusion and exclusion criteria in the protocol at the same time. Randomized grouping ensures that, except for treatment factors, other non-treatment factors that may have confounding effect are kept consistent in each group as far as possible, so as to ensure the balance of baseline of each group; randomized-grouping allows each subject to have equal opportunity to be assigned to the test group or control group.
- (4) Incomplete blinding: Since the investigational medical device and the control medical device are different in appearance, while the subjects are under anesthesia during the operation, the grouping arrangement can not be known. Therefore, the method of incomplete blinding is used, that is, the investigators knows the grouping result, while the subject does not know the grouping result. The blinding method can minimize the bias caused by "placebo effect" and investigator bias; for the less precise observation indicators, it can significantly reduce the bias; and make the evaluation of adverse reactions by investigators and subjects more objective.
- (5) Parallel positive control: The investigational medical device has the mature application technology with many similar products that are marketed at home and abroad. It has been used in clinical practice for many years, with exact effect and predictable occurrence of adverse events. Therefore, parallel positive control is adopted in this clinical trial.
- (6) Non-inferiority test: To evaluate whether the main effectiveness evaluation indicator "success rate of anastomosis" of the Disposable Powered Articulating Endoscopic Linear Cutter Stapler manufactured by Fengh Company is non-inferior to the similar product manufactured by Johnson & Johnson Company in gastrointestinal tissue cutting and anastomosis. It is expected that the test product is similar to the control product in performance. There is no significant difference in the expected results between the two groups

in the primary efficacy indicator of "success rate of anastomosis" during gastrointestinal tissue cutting and anastomosis. Therefore, the non-inferiority test is adopted.

8.1.4 Measures for reducing and avoiding bias

- (1) Before the start of the study, the sponsor shall provide relevant training for the investigators participating in the study to ensure that the investigators fully understand the study process and are familiar with the operation of the study device; during the study, the investigators shall operate in strict accordance with the operating methods and procedures in the study protocol, and the clinical trial monitor shall do a good job in quality control and monitoring to ensure that the investigators operate and implement in strict accordance with the study protocol. The above measures shall be implemented throughout the implementation phase of the study to reduce errors or operational errors.
- (2) Subjects shall be screened in strict accordance with the clinical diagnostic criteria, as well as the inclusion and exclusion criteria of the trial protocol to reduce selection bias.
- (3) Total laparoscopic digestive tract reconstruction is difficult to operate, which should be carried out in centers with rich experience in laparoscopic surgery. In view of the learning curve of laparoscopic surgery, doctors can be more proficient based on at least 50 cases^[2]. The operating surgeon of laparoscopic surgery is recommended to be experienced in at least 100 cases of open surgery as the operator and 50 cases of laparoscopic surgery as the primary assistant.
- (4) When the clinical trial is completed, the data storage and collation shall be done well. When data problems are found, the data analyst shall check and confirm the data through the data clarification form to avoid recording errors.

8.1.5 Investigational medical device and control medical device or control diagnosis and treatment method

See the corresponding IFU for the diagnosis and treatment method with the investigational medical device and the reference medical device. In addition, subjects may use circular stapler or other types of staplers during the clinical trial. If these staplers are used, the investigators should truthfully record the model of these staplers and staple cartridge for reference.

When subjects experience adverse events related to the stapler, the investigators should truthfully judge the correlation between adverse events and the test device.

8.1.5.1 Information of circular stapler

Product name	ILS Curved and Straight Intraluminal Staplers		
Specification/model	CDH21A, CDH25A, CDH29A, CDH33A, SDH21A, SDH25A, SDH29A, SDH33A		

wire i mestomosis	
Registration No	. GXZJ 20152652249
Manufacturer	Ethicon Endo-Surgery, LLC
	The product is composed of orange display area, trocar, reload, safety indicator window,
	adjusting knob, safety device, firing trigger, staple board, anti-trocar, anti-trocar
Structural	protective cover, staple anvil head, knotting groove, locking spring leaf and staple anvil
composition	rod. The material of stapler is medical stainless steel, the material of knob is
	polycarboxylate, and the material of staple is titanium alloy. Radiation sterilization,
	single use.
Scope	of This product is used for end-to-end, end-to-side and side-to-side anastomosis of the
application	whole digestive tract.
	If the subjects in the test group or control group (only for the subjects at rectal site) need
Requirements use	to use the circular stapler during the clinical trial, the investigators shall uniformly use
	the circular stapler (Johnson & Johnson brand, model CDH25A or CDH29A) uniformly
	provided by Fengh Company. For the using process, records shall be truthfully kept for
	reference.

8.1.6 Selection of Subjects

8.1.6.1 Clinical trial indications

At present, the Disposable Powered Articulating Endoscopic Linear Cutter Stapler can be used for "a variety of open or minimally invasive surgeries in general surgery, obstetrics and gynecology, urology, thoracic surgery and pediatrics. They can be used with suture or tissue staple supporting material. They also can be used for transection and excision of liver parenchyma (hepatic vascular system and bile duct structure), pancreas, kidney and spleen.

However, according to the *Guidelines for Technical Review of Endoscopic Stapler Registration*, "the surgical site and/or tissue type and thickness selected for clinical trial shall cover the intended clinical applicable scope of the product under application". Therefore, gastrointestinal surgery is selected for the clinical trial.

Therefore, the indication of this clinical trial is: "gastrointestinal tissue cutting and anastomosis".

8.1.6.2 Inclusion criteria

Subjects meeting all of the following conditions only can be included:

- (1) Subjects are aged 18-70 years (inclusive), male or female;
- (2) Subjects are scheduled to accept gastrointestinal tissue cutting and anastomosis;
- (3) Subjects or their guardians are able to understand the purpose of the study, show adequate compliance with the trial protocol, and sign an ICF.

8.1.6.3 Exclusion criteria

Subjects meeting any of the following conditions can not be included:

- (1) Subjects who are scheduled to receive gastrointestinal emergency surgery;
- (2) Subjects with moderate malnutrition (BMI \leq 17 kg/m²) and severe anemia (Hb \leq 60 g/L);
- (3) Subjects with a BMI \geq 28 kg/m²;
- (4) Subjects with platelet (PLT) $< 60 \times 10^{9}$ /L or international normalized ratio (INR) > 1.5;
- (5) Subjects with a forced expiratory volume in one second (FEV1)/predicted value ≤ 50%, or a forced expiratory volume in one second (FEV1)/forced vital capacity (FCV) ≤ 60%;
- (6) Subjects with ejection fraction $\leq 50\%$;
- (7) Subjects with important organ failure or other serious diseases (e.g., the subject's aspartate aminotransferase (AST), alanine aminotransferase (ALT), or serum creatinine (Scr) is more than 3 times of the upper limit of normal before surgery; the subject's fasting blood glucose value before surgery is ≥ 10.0 mmol/L);
- (8) Subjects who are pregnant or lactating women;
- (9) Subjects who have participated in other drug or device clinical trials within 3 months prior to the trial;
- (10)Other situations not suitable for inclusion judged by the investigators.

8.1.7 Study termination criteria

Study termination refers to that the clinical study has not been completed according to the protocol, and all clinical studies are stopped halfway. The purpose of terminating the clinical study is to protect the rights and interests of the subjects and ensure the quality of clinical study. Except for Item 6 below, the sponsor and the investigators shall jointly negotiate whether to terminate the trial:

- (1) If serious safety problems occur during the clinical study, the clinical study should be terminated in a timely manner;
- (2) If the product is found to have no clinical value during the clinical study, the clinical study shall be terminated;
- (3) In the process of clinical study, it is found that the clinical study protocol has major errors and it is difficult to evaluate the product effect; or the protocol has serious deviation in the implementation, in which it is difficult to evaluate the product effect if the study is continuously to be conducted, , the clinical study shall be terminated;
- (4) The sponsor requests to terminate the study (for reasons, e.g., financial, etc.);
- (5) The clinical trial institutions and investigators fail to comply with the laws and regulations related to clinical trial and clinical trial protocol, and fail to make correction after being pointed out, resulting in

serious situations or failure to change.

(6) NMPA orders to terminate the clinical study for some reason(s).

After the study is terminated, the investigators should continue to provide appropriate treatment for the subjects from the perspective of protecting the rights and interests of the subjects, and inform the subjects of the treatment received during the trial and related treatment in detail. The subject data continues to be acceptable for evaluating the safety of the product.

The investigators should timely feed back the termination of the subject study to the sponsor.

8.1.8 Enrollment time

It is estimated that the first subject will be enrolled in June 2018. The total enrollment time is 6 months, and the trial end time for the last subject will be December 2018.

8.1.9 Expected duration of clinical trial and the reasons for determination

The expected enrollment time for the first subject is June 2018. The enrollment time for subjects is 6 months. The time for the last subject to complete the trial is December 2018. The time for statistical analysis and preparation of study summary report after the completion of clinical trial is 2 months, and the total clinical study period is 8 months.

8.1.10 Expected duration of participation of each subject

The expected screening period from signing the ICF to enrollment for each subject is 7 days, and the postoperative follow-up period is about 30 days. The total subject observation period is 37 days. If a subject experiences an adverse event during the clinical trial, the outcome of the adverse event needs to be observed.

8.1.11 Number of subjects required for clinical trial

The total sample size is 164. See Section 9.2 for details.

8.1.12 Drop-out criteria and treatment

- (1) Definition of drop-out: All the subjects who have signed the ICF and passed screening to enter the clinical trial, no matter when or when they withdraw from the study, will be called drop-out cases as long as they have not completed the observation period specified in the protocol.
- (2) Drop-out criteria:
- a) The subject is unwilling or impossible to continue the clinical trial for any reason, and the clinical trial is terminated by putting forward a request for withdrawal from the clinical trial to the investigator;
- b) The subject is lost to follow-up due to no treatment or examination although the subject does not

explicitly withdraw from the clinical trial;

- c) If the subject experiences a serious adverse event (SAE), the investigator should withdraw the subject from the clinical trial;
- d) Poor subject compliance.

For all the dropout cases, it is necessary to fill in the summary form of completion of clinical trial in the case report form and analyze the reasons for dropout. When a subject dropped out, the investigator should contact the subject as far as possible, ask the reason and record the last clinical symptom, and complete the evaluation items that could be completed. When withdrawing from the study due to adverse events, the investigator should take appropriate treatment measures according to the actual situation of the subject.

When a subject or his/her guardian actively requests to withdraw from the trial, the subject or his/her guardian should be asked that whether the subject's previous data can be continuously used in the clinical trial, and whether the results can be recorded in the original records. When no enquiry is performed, the data are available by default.

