Technical Review of Endoscopic Stapler Registration issued by China Food and Drug Administration on March 13, 2017, the "incidence of anastomotic leakage" is selected as a safety evaluation indicator for such products.

Evaluation time: From the end of surgery to the end of follow-up.

Evaluation method: Patients with at least one of the following items are considered as anastomotic leakage: A. imaging examination, such as gastrointestinal radiography, confirms anastomotic leakage; B. fecal substances appearing in the abdominal drainage tube or incision, in which other sources of intestinal tract can be excluded; C. reoperation exploration confirms anastomotic leakage; D. abdominopelvic abscess beside the anastomosis. Anastomotic leakage is divided into 3 grades according to the severity: Grade A: no special treatment is required; Grade B: active treatment is required, but no reoperation is required; Grade C: reoperation is required.

Formula: Incidence of anastomotic leakage = eligible subjects in each group/total number of subjects in this group \times 100%

Precautions: Necessary records should be kept for the treatment of anastomotic leakage.

(4) Incidence of anastomotic stricture

Justification for Selection: Anastomotic stricture is a common complication of gastrointestinal anastomosis, which will increase risks to subjects. Therefore, "the incidence of anastomotic stricture" is selected as one of the indicators to evaluate the product safety.

Evaluation time: From the end of surgery to the end of follow-up.

Evaluation method: The clinician judges whether the subject has an anastomotic stricture based on the symptoms, signs, endoscopy, angiography, etc.

Formula: Incidence rate of anastomotic stricture = eligible subjects in each group/total number of subjects in the group \times 100%

(5) Incidence of anastomotic stricture infection

Justification for Selection: Anastomotic stricture infection is a common complication of gastrointestinal anastomosis, which will increase risks to subjects. Therefore, "the incidence of anastomotic stricture infection" is selected as one of the indicators to evaluate the product safety.

Evaluation time: from the end of surgery to the end of follow-up.

Evaluation method: The clinician judges whether the subject has a staple line infection based on the symptoms, signs, endoscopy, angiography, etc.

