Formula: Incidence rate of anastomotic stricture infection = eligible subjects in each group/total number of subjects in the group \times 100%

(6) Incidence of SAE (serious adverse event)

Evaluation time: During the whole clinical trial process.

Evaluation method: Serious adverse event refers to an event occurs in the process of clinical trials, which results in death or serious deterioration of health, including fatal disease or injury, permanent damage to the body structure or function, requiring hospitalization or prolonging the hospitalization, requiring medical or surgical intervention to avoid the permanent damage to the body structure or function; results in fetal distress, fetal death or congenital abnormality, congenital defect, etc.

Formula: SAE incidence = number of subjects with SAE in this group/number of all subjects in this group \times 100%.

Precautions: The adverse events related to the anastomotic stoma during clinical trial shall be considered as serious adverse events. Since "anastomotic stoma repair" may be associated with "anastomotic stoma dehiscence", the "anastomotic stoma repair "is not repeatedly considered a serious adverse event.

(7) Incidence of AE (adverse event)

Evaluation time: During the whole clinical trial process.

Formula: Incidence of adverse events = number of subjects with adverse events in this group/number of all subjects in this group \times 100%.

Definition: An adverse event is any untoward medical occurrence in a clinical investigation, whether or not related to the device. It is necessary to analyze the postoperative vital signs and laboratory tests (blood routine, biochemical indicators, etc.).

(8) Incidence of device defects

Measurement time: During the whole process of clinical trial.

Calculation formula: Incidence of device defect = number of device defects/total number of devices × 100%.

Precautions: A test device defect that occurs during the course of a clinical trial. "Staple pop" due to human factors (e.g., incorrect reload selection) is not a defect of the device.

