14.1.3 Reporting and handling of adverse events

All the adverse events and serious adverse events observed in the clinical trial should be clearly filled in the adverse event column of case report form. The duration of adverse event (i.e., the date of occurrence and disappearance of adverse event), severity, relationship with the clinical trial, and corresponding treatment and other handling measures should be recorded. Subjects occurring such event shall be followed up to end of the trial or the adverse event outcome.

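### Withdrawing every subject with an SAE, when anastomosis-related adverse events all count as SAEs, conflicts with the protocol's own follow-up rules and can make Day 7 and Day 30 data missing because of the outcome

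*Combined protocol and SAP*

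**What the plan says.** Section 8.1.12 lists, among the drop-out criteria, item c): "If the subject experiences a serious adverse event (SAE), the investigator should withdraw the subject from the clinical trial". It sets no limit on type, timing or relation to the device. Item (1) of the same section says that subjects who leave early "will be called drop-out cases as long as they have not completed the observation period specified in the protocol". For every drop-out the investigator is to make contact where possible, "ask the reason and record the last clinical symptom, and complete the evaluation items that could be completed".

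Section 8.1.16(6) widens the SAE category: "The adverse events related to the anastomotic stoma during clinical trial shall be considered as serious adverse events". Its only exception is that repair of the anastomosis "is not repeatedly considered a serious adverse event".

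Three other places require continued observation:

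- Section 8.1.10: "If a subject experiences an adverse event during the clinical trial, the outcome of the adverse event needs to be observed".
- Section 14.1.3, on adverse and serious adverse events alike: "Subjects occurring such event shall be followed up to end of the trial or the adverse event outcome".
- Section 8.1.16, for leakage and stricture: "Evaluation time: From the end of surgery to the end of follow-up". Bleeding and infection have the same window.

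Section 11.2 names too many SAE withdrawals as a possible cause of trial failure, so the plan expects item c) to be used.

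**The concern.** The device is used in one operation. Withdrawal after surgery therefore ends no exposure to it; what it can reduce is data. The subjects affected are those with the events that the safety comparison is meant to measure.

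A site that applies item c) strictly may not bring such a subject back for Day 7 or Day 30. A site that applies 14.1.3 will keep following. Five centers can act differently, each citing the protocol. Where follow-up is cut short, data are missing because of the outcome, and no analysis can recover them afterwards.

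**Working it through.** **1. The plan's own figures.** Inputs from section 9.2.1: success 97% (taken for both arms), margin 10%, one-sided alpha 0.025, power 80%.

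- Uncorrected size per group: 2 × 0.97 × 0.03 × (1.960 + 0.842)² / 0.10² = 45.7.
- With the correction: (45.7/4) × [1 + √(1 + 4/(45.7 × 0.10))]² = 64.1, so 65.
- With 20% dropout: 65 / 0.80 = 81.25, so 82 per group and 164 in total.

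The stated size reproduces and is not in dispute.

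**2. The chain of rules.**

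- A postoperative anastomotic bleed, leak, stricture or infection is an anastomosis-related adverse event, hence an SAE (8.1.16(6)).
- An SAE leads to withdrawal (8.1.12(2)c)).
- A subject withdrawn before Day 30 has not completed the observation period and is a drop-out (8.1.12(1)).
- The same subject is to be followed to the outcome or the end of the trial (8.1.10, 14.1.3), and the endpoint windows stay open to the end of follow-up (8.1.16).

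The last step cannot be squared with the withdrawal unless data collection continues after it, and the protocol does not say that it does.

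**3. How many subjects.** Section 14.1.5 quotes a literature leakage incidence of 4% to 15%.

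- Lower end: 164 × 0.04 = 6.6, about 7 subjects (82 × 0.04 = 3.3 per group).
- Upper end: 164 × 0.15 = 24.6, about 25 subjects (82 × 0.15 = 12.3 per group).

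These counts are for leakage alone. Bleeding, stricture and infection would add to them, less any overlap.

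**4. What happens to the missing values.** Section 9.7.2(7) fills missing safety values with the worst case. A subject withdrawn after a leak could thus be scored with a bleed, stricture or infection that nobody observed. If every leak subject lost all later assessments and had none of these events recorded, each of those three rates would rise by up to the leak rate itself, 3.3/82 = 4% to 12.3/82 = 15%. This is an upper bound under that assumption.

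Section 9.7.2(4) leaves missing secondary values unestimated. Healing time is the most exposed, because it is collected at the Day 30 visit (8.2.7.4).

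**5. The primary endpoint.** Anastomosis success is scored during surgery (8.1.15.1), so a later withdrawal does not remove the observation. Section 9.4, however, lists failure to complete follow-up among the conditions that may be confirmed as a serious violation and keep a subject out of the primary analysis. Section 9.9 names the PPS, which excludes serious deviations, as primary for efficacy analysis. The principal investigator confirms such violations, and investigators know the allocation (8.2.4). Exclusion is possible but not required.

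**The case against.** The strongest reply is that the protocol nowhere says observation stops. Section 8.1.12 asks for whatever can be completed, and 14.1.3 covers SAEs explicitly. That stands: ended observation is one reading of an ambiguity. But the completion clause is best effort and does not require the Day 7 and Day 30 visits. Section 14.1.3 can be met once the triggering event resolves, which does not secure the later assessment of the other endpoints.

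A reader might infer more, in four ways that the documents do not support:

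- **That the safety comparison is tilted in favor of the worse device.** Worst-case filling, applied as written, penalizes the arm with more withdrawals. AE and SAE incidence are counted per subject, and the triggering event is already recorded. Whether a blank is treated as missing or as no event is left to the data review (9.7.2).
- **That a staple-line failure seen in surgery makes its own subject a drop-out.** The bleeding and leakage safety endpoints begin after surgery. No section says that an intraoperative primary failure must also be recorded as an adverse event, and repair is not counted again as an SAE.
- **That leakage withdrawals use up a stated share of the 20% dropout allowance.** Section 9.4 defines that 20% as subjects excluded from the primary analysis; 8.1.12 means subjects who do not complete observation. A ratio of the two mixes definitions.
- **That the false-positive rate of the non-inferiority test rises by a known amount.** That depends on the share of primary failures excluded, which the documents do not give.

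Two losses are also smaller than they look. Section 14.1.5 places most strictures later than one month after surgery, largely outside the window in any case. Flatus, bowel movement and semi-liquid diet are recorded only up to discharge (8.1.15.2), so they may be captured despite withdrawal.

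**Conclusion.** The contradiction is real and rests on the protocol's own wording. Followed as written, 8.1.12(2)c) with 8.1.16(6) allows outcome-dependent missing data in the postoperative safety endpoints, healing time and possibly the other recovery times. About 7 to 25 of 164 subjects would meet the withdrawal rule through leakage alone, if the quoted 4% to 15% applies to this population and each leak is recorded as an adverse event. How many would actually lose Day 7 or Day 30 data depends on how sites read the conflict.

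The direction of the safety bias is uncertain. The primary outcome is at risk only through exclusion from the PPS.

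**What to change.** Reconcile 8.1.10, 8.1.12, 8.1.16 and 14.1.3 so that they give one instruction on data collection. State that an SAE, or withdrawal under 8.1.12(2)c), does not by itself end collection of the scheduled Day 7 and Day 30 data unless the subject withdraws consent. State also that it does not by itself exclude the subject's observed primary outcome from the analysis, and align 9.4 and 9.9 with this.

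This concerns data only. Clinical management of the event stays with the investigator, and no view is taken on which clinical rule for subjects with an SAE is right.

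The cost is essentially one sentence and site retraining. No visits are added, because both are already scheduled for every subject (8.2.7).
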